9.5. Interim Analyses

For each analysis (3 stages in Part 1 and the formal interim and final analysis in Part 2), the data cutoff will be the time point when the last participant in the respective analysis has been treated for a minimum of 3 cycles (Part 1) or 4 cycles (Part 2) of the combination therapy.

NOTE: Part 2 of the study will not be conducted because further development of this regimen (cusatuzumab in combination with azacitidine) in patients with unfit AML will not be pursued due to the evolving treatment landscape in AML.

Study Part 1

Part 1 of the study consists of 3 stages of monitoring to select a dose schedule. The cumulative number of participants for each dose group at each of the 3 stages are 15, 30, and 50, respectively. At each stage, each dose group's response rate will determine independently (without formal statistical comparison to the other group) if that dose group will be stopped or continued into the next stage or into study Part 2. Only 1 dose group will be selected for Part 2. The statistical criteria for such a determination will be based on the number (and percentage) of participants in each dose group achieving CR.

The purpose of the 3-stage monitoring in Part 1 is to select, or to eliminate a dose, which will be based on the Pocock beta-spending function with an overall beta level of 10% allocated to the 3 stages with respective and cumulative sample sizes of 15 (30%), 30 (60%), and 50 (100%) participants per group. Per this approach, the statistical decision criteria and corresponding inferences are summarized in Table 7, where 2 possible outcomes resulting in a stop or continuation decision, respectively, are presented for each stage.

The statistical criteria shown in Table 7 ensure that the false negative error rate (ie, the probability of a stopping decision, when the true CR rate is $\geq 35\%$) is $\leq 6\%$ at any stage; or equivalently, the upper limit of the 1-sided $>94\%$ confidence interval (CI) of the observed CR rate is $< 35\%$ (which means that a CR rate of 35% or greater has been statistically ruled out). It's important to control the false negative error rate at a low level when the number of participants is small to ensure that a stopping decision will not be made unless it is statistically convincing that a CR rate of $\geq 35\%$ has been ruled out. The false positive error rate (ie, the probability of a continuation decision, when the true CR rate is $\leq 20\%$) is also assessed, but controlling the false positive error rate at a low level is not of a concern, hence is not applied in this circumstance (Table 8).

Table 7: Statistical Decision Parameters for Study Part 1: Observed CR, 1-Sided Confidence Interval (CI), and Statistical Decision

	Number (%) of Observed CR	1-Sided CI Upper Bound ¹ (%)	Decision	False Negative Error ²	False Positive Error ³
Stage 1, n=15	1 (6.7)	26.7	Stop	≤4%	NA
	2 (13.3)	34.9			
	3 (20.0)	42.3	Continue to Stage 2	NA	≤50%
	4 (26.7)	49.3			
Stage 2, n=30	5 (16.7)	30.5	Stop	≤5%	NA
	6 (20.0)	34.3			
	7 (23.3)	37.9	Continue to Stage 3	NA	≤32%
	8 (26.7)	41.5			
Stage 3, n=50	11 (22.0)	32.3	Stop	≤6%	NA
	12 (24.0)	34.4			
	13 (26.0)	36.6	Continue to Part 2	NA	≤14%
	14 (28.0)	38.7			

¹ 96%, 95%, and 94% for Stage 1, 2, and 3, respectively.

² False negative error: probability of a “stop” decision, when the true CR rate is ≥35%.

³ False positive error: probability of a “continue” decision, when the true CR rate is ≤20%.

Note: All statistical inferences are based on Wilson Score statistics without continuity correction.

If the number of participants at each stage is not exactly as specified in Table 7 the Pocock beta-spending function with an overall beta level of 10% will be adjusted based on the actual number participants.

Per statistical criteria specified in Table 7, certain operating characteristics of particular interest are presented in Table 8, showing the probability of making a correct decision.

The above statistical criteria for Part 1 will be served as guidance; the totality of the data including other efficacy outcomes (eg, duration of CR), available safety, and PK/PD data will be considered in making a decision at each stage. If both dose schedules warrant proceeding into study Part 2 per the above statistical criteria, only one dose schedule will be extended into Part 2 based on the observed CR rate as well as available data of other efficacy, safety, and PK/PD.

Table 8: Operating Characteristics of Particular Interest

Study Part 1, probability that:	True CR Rate of Dose (20 mg/kg, 10mg/kg)		
	(35%, 35%)	(35%, 20%)	(20%, 20%)
At least one dose schedule continues into Part 2	98.4%	--	--
20 mg/kg continues into Part 2, 10 mg/kg does not	--	74.3%	--
Neither dose schedule continues into Part 2	--	--	72.1%

Study Part 2

For study Part 2, one interim analysis of CR rate is planned to include 80 participants. The null hypothesis of a CR rate of 20% will be rejected if the 1-sided nominal p-value is ≤ 0.01221 . If the null hypothesis is not rejected at this interim analysis, the final analysis will be performed with 100 participants, and the null hypothesis will be rejected if the 1-sided nominal p-value is ≤ 0.02144 . The O'Brien-Fleming alpha-spending, and the Wilson Score test without continuity correction are to be implemented for the interim and final analyses.

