1.5. Interim Analyses

For each analysis (3 stages in Part 1 and the formal interim and final analysis in Part 2), the data cutoff will be the time point when the last participant in the respective analysis has been treated for a minimum of 3 cycles (Part 1) or 4 cycles (Part 2) of the combination therapy.

Study Part 1

Part 1 of the study consists of 3 stages of monitoring to select a dose schedule. The cumulative number of participants for each dose group at each of the 3 stages are 15, 30, and 50, respectively. At each stage, each dose group's response rate will be determined independently (without formal statistical comparison to the other group) if that dose group will be stopped or continued into the next stage or into study Part 2. Only 1 dose group will be selected for Part 2. The statistical criteria for such a determination will be based on the number (and percentage) of participants in each dose group achieving CR.

The purpose of the 3-stage monitoring in Part 1 is to select, or to eliminate a dose, which will be based on the Pocock beta-spending function. The overall beta level is chosen as 10%, allocated to the 3 stages with respective and cumulative sample sizes of 15 (30%), 30 (60%), and 50 (100%) participants per group; the corresponding nominal significance level (calculated against the alternative hypothesis of 35% CR rate) are 0.04157, 0.04618, and 0.05632. Per this approach, the statistical decision criteria and corresponding inferences are summarized in [Table 1](#), where 2 possible outcomes resulting in a stop or continuation decision are presented for each stage.

The statistical criteria shown in [Table 1](#) ensure that the false negative error rate (ie, the probability of a stopping decision, when the true CR rate is $\geq 35\%$) is $\leq 6\%$ at any stage; or equivalently, the upper limit of the 1-sided $>94\%$ confidence interval (CI) of the observed CR rate is $<35\%$ (which means that a CR rate of 35% or greater has been statistically ruled out). It's important to control the false negative error rate at a low level when the number of participants is small to ensure that a stopping decision will not be made unless it is statistically convincing that a CR rate of $\geq 35\%$ has been ruled out. Since all the analyses in study Part 1 are futility evaluations without the intention to stop for efficacy, the overall type I error of the entire study is not inflated.

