If the number of participants at each stage is not exactly as specified in [Table 1](#), the Pocock beta-spending function with an overall beta level of 10% will be adjusted based on the actual number participants.

The above statistical criteria for Part 1 will be served as guidance; the totality of the data including other efficacy outcomes (eg, duration of CR), available safety, and PK/PD data will be considered in making a decision at each stage. If both dose schedules warrant proceeding into Part 2 per the above statistical criteria, only one dose schedule will be extended into Part 2 based on the observed CR rate as well as available data of other efficacy, safety, and PK/PD.

Table 1: Statistical Decision Parameters for Study Part 1: Observed CR, 1-Sided Confidence Interval (CI), and Statistical Decision

	Number (%) of Observed CR	1-Sided CI Upper Bound ¹ (%)	Decision	False Negative Error ²	False Positive Error ³
Stage 1, n=15	1 (6.7)	26.7	Stop	≤4%	NA
	2 (13.3)	34.9			
	3 (20.0)	42.3	Continue to Stage 2	NA	≤50%
	4 (26.7)	49.3			
Stage 2, n=30	5 (16.7)	30.5	Stop	≤5%	NA
	6 (20.0)	34.3			
	7 (23.3)	37.9	Continue to Stage 3	NA	≤32%
	8 (26.7)	41.5			
Stage 3, n=50	11 (22.0)	32.3	Stop	≤6%	NA
	12 (24.0)	34.4			
	13 (26.0)	36.6	Continue to Part 2	NA	≤14%
	14 (28.0)	38.7			

¹ 96%, 95%, and 94% for Stage 1, 2, and 3, respectively.

² False negative error: probability of a “stop” decision, when the true CR rate is ≥35%.

³ False positive error: probability of a “continue” decision, when the true CR rate is ≤20%.

Note: All statistical inferences are based on Wilson Score statistics without continuity correction.

Study Part 2

For Part 2, 1 interim analysis of CR rate is planned to include 80 participants. The null hypothesis of a CR rate of 20% will be rejected if the 1-sided nominal p-value is ≤0.01221. If the null hypothesis is not rejected at this interim analysis, the final analysis will be performed with 100 participants, and the null hypothesis will be rejected if the 1-sided nominal p-value is ≤0.02144. The O’Brien-Fleming alpha-spending, and Wilson Score test without continuity correction is to be implemented for the interim and final analyses.

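### Protocol Table 7 and SAP Table 1 label score-approximation values as decision probabilities: the exact false-stop rates at a true CR rate of 35% are 6.2/5.9/6.6% per look (caps 4/5/6%) and 12.6% overall (stated beta 10%), and Table 8 fits Section 9.5 but not Section 4.1

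*Protocol*

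**What the plan says.** Protocol Section 9.5 sets three futility looks per dose group, at cumulative sizes of 15, 30 and 50. According to the SAP, "The overall beta level is chosen as 10%, allocated to the 3 stages", and "the corresponding nominal significance level (calculated against the alternative hypothesis of 35% CR rate) are 0.04157, 0.04618, and 0.05632". Table 7 and SAP Table 1 imply a stop at 2 or fewer CRs of 15, 6 or fewer of 30, and 12 or fewer of 50.

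The error columns print a false-negative error of at most 4%, 5% and 6%, and a false-positive error of at most 50%, 32% and 14%. Footnote 2 reads "False negative error: probability of a “stop” decision, when the true CR rate is ≥35"%, and footnote 3 gives the matching definition for a continue decision at 20% or less. The text says "The statistical criteria shown in Table 7 ensure that the false negative error rate" is at most 6% at any stage, "or equivalently, the upper limit of the 1-sided" interval (level above 94%) lies below 35%. A note under the table adds: "All statistical inferences are based on Wilson Score statistics without continuity correction".

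Table 8, in the protocol only, gives the probability of a correct decision in three scenarios: 98.4%, 74.3% and 72.1%. The last is for the outcome "Neither dose schedule continues into Part 2" when both doses have a true rate of 20%.

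Section 9.5 judges each dose group independently. Section 4.1 says that once one group is dropped at Stage 1 or 2, the other moves straight to Part 2 with no further Part 1 evaluation.

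**The concern.** A score-test tail area is a normal approximation, whereas the chance that a counting rule tells the team to stop is a binomial probability. At n = 15 to 50 the two differ materially. The columns are defined as the second but filled from the first.

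This bears on the purpose the protocol itself gives for the rule, which is to keep false stops rare while numbers are small. The largest excess over a cap is at Stage 1. A reader who takes the columns at face value gets the wrong error rates for the planned rule.

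The conflict between Sections 4.1 and 9.5 is a second matter. The two sections describe different stopping schemes with different operating characteristics, and the protocol does not say which one Table 8 describes.

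**Working it through.** **Inputs.** Stage sizes 15/30/50, stop counts 2/6/12, CR rates 20% and 35%, and one-sided CI levels 96/95/94% come from Protocol 9.5 and Table 7. The nominal levels come from SAP 1.5.

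**1. The plan's own figures reproduce under its method.**
- Wilson upper bounds at the stop counts are 34.9/34.3/34.4%, as printed. The other nine printed bounds also match.
- Pocock-type spending, 0.1 × ln(1 + (e − 1)t) at t = 0.3, 0.6 and 1, gives 0.0416/0.0709/0.1000. Under a trivariate normal the SAP nominal levels give the same cumulative values.
- Score tail at 35%, Φ((s − 0.35n)/√(n × 0.35 × 0.65)): z = −1.76, −1.72, −1.63, giving 3.9/4.2/5.1%. All lie inside the caps.
- Score tail at 20% for the first continue count (3, 7, 13): z = 0, 0.46, 1.06, giving 50.0/32.4/14.4%. These are the printed false-positive limits.

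**2. Exact per-look probabilities.**

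| Stage | Stop if | P(stop) at 35%, exact | Cap | P(continue) at 20%, exact | Printed |
|---|---|---|---|---|---|
| 1 | ≤2/15 | 6.2% | 4% | 60.2% | 50% |
| 2 | ≤6/30 | 5.9% | 5% | 39.3% | 32% |
| 3 | ≤12/50 | 6.6% | 6% | 18.6% | 14% |

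Stage 1 shows the cause. Three of 15 is exactly 20%, so the uncorrected score gives z = 0 and 50%, while P(X ≥ 3 | 15, 0.20) = 60.2%.

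**3. Exact sequential probabilities.** Carrying the binomial distribution forward through the looks, the first-stop probabilities are:
- at 35%: 0.0617 + 0.0335 + 0.0312 = 0.1265 (12.6% from unrounded values), against the stated 10%. Normal theory at the same cut-offs gives 9.3%;
- at 20%: 0.3980 + 0.2556 + 0.1963 = 0.8499, so 15.0% are still continuing after Stage 3.

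**4. The equivalence clause.** A Wilson bound below 35% is equivalent to a small score tail, not to a small exact stop probability. Exact (Clopper-Pearson) upper bounds at the stop counts and the table's own levels are 37.7/35.7/35.3%, all above 35%.

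**5. Table 8.**

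| Scenario | Printed | Section 9.5 (independent groups) | Section 4.1 |
|---|---|---|---|
| 35%, 35%: at least one continues | 98.4% | 1 − 0.1265² = 98.4% | 1 − (0.0617² + 0.0335² + 0.0312²) = 99.4% |
| 35%, 20%: only the 35% dose continues | 74.3% | 0.8735 × 0.8499 = 74.2% | 0.9383 × 0.3980 + 0.9047 × 0.2556 + 0.8735 × 0.1963 = 77.6% |
| 20%, 20%: neither continues | 72.1% | 0.8499² = 72.2% | 0.3980² + 0.2556² + 0.1963² = 26.2% |

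The Section 4.1 column assumes both groups are reviewed at the same looks and the criteria are applied mechanically. The printed 98.4% already implies a per-dose false-stop rate of √0.016 = 12.6%. A rate of 10% would give 1 − 0.10² = 99.0%.

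**6. Sensitivity to stage size.** Each size was moved by up to 2 from plan, with the SAP nominal levels held fixed (an assumption). The exact per-look false-stop rate then ranges over about 2–6.2%, 3.0–5.9% and 4.2–6.6%. Over all 125 combinations the cumulative rate runs from 6.8% to 12.6%, with a median of 9.2%. The planned sizes give the top of each range.

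**The case against.** The best defence is that the method is disclosed. Within the score framework the caps are valid upper bounds, and the tail area and the Wilson bound are equivalent. The false-negative entries can equally be read as the rounded SAP nominal levels (4.2/4.6/5.6%). On this view only a qualifier such as nominal is missing, and Clopper-Pearson bounds are just a more conservative choice of interval. That explains where the numbers come from. It does not make them probabilities of a decision, which is how footnotes 2 and 3 define them, or support a claim to ensure them.

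A second point is that first-stop probabilities suit stagewise spending better. They are 6.2/3.4/3.1%, so Stages 2 and 3 meet their caps. This stands, but Stage 1 still exceeds both its 4% cap and the general 6%, and the cumulative 12.6% is the same on either reading.

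Third, much of the excess is binomial discreteness at exactly 15/30/50. In about 70% of the nearby size combinations the cumulative rate is 10% or less, and the protocol allows for this: "If the number of participants at each stage is not exactly as specified in Table 7", the spending is adjusted. This also stands. The actual sizes are not given, so nothing here describes the boundaries actually applied. The printed tables, however, are for the planned sizes.

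Finally, the consequences are small. The criteria were guidance beside the totality of the data, false-positive control was expressly not a goal, and Table 8 already gives near-exact overall probabilities. SAP 1.6 records that all three stages were analysed, Part 2 did not follow, and Part 1 is summarised descriptively. This limits the weight of the point but does not correct the figures.

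**Conclusion.** The concern holds. For the planned 15/30/50 rule, with binomial responses and independently judged groups, the false-stop rate at 35% is 6.2/5.9/6.6% per look against 4/5/6%, and 12.6% cumulatively against 10%. Stages 1 and 3 also exceed the general 6% limit per look. The false-positive column is understated by 10.2, 7.3 and 4.6 percentage points (60.2 − 50, 39.3 − 32, 18.6 − 14).

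The Wilson bounds, SAP nominal levels and cut-offs are correct under the stated method; the error is in what the columns and text say those values are. Table 8 is right for Section 9.5 and inconsistent with Section 4.1. No estimate or reported interval is affected, so this is a correction that should be made, not one on which the trial's results depend.

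**What to change.** Correct SAP 1.5 and SAP Table 1, and add a study-report note for Protocol Tables 7 and 8:

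1. Replace the error columns with the exact values, labelled per look, or relabel the printed values as nominal score levels with the exact values beside them.
2. Change the 6% limit in the text to the exact per-look maximum for the planned sizes (at most 7%). Remove the equivalence wording so that the Wilson interval criterion stands as a separate statement.
3. Report the 12.6% cumulative false-stop rate beside the nominal 10% beta, noting that it assumes independently judged groups.
4. Reconcile Section 4.1 with Section 9.5 and state which rule Table 8 follows.
5. State that the figures apply to the planned stage sizes and that the criteria were guidance.

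The cost is text and table figures only. Table 8 is not in the SAP, so it needs only the study-report note. No threshold, data or estimate changes.

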9.6. Data Review Committee

A Data Review Committee (DRC) will be established as noted in Committees Structure in Appendix 3 Section 10.3, Regulatory, Ethical, and Study Oversight Considerations.

10. SUPPORTING DOCUMENTATION AND OPERATIONAL CONSIDERATIONS

10.1. Appendix 1: Abbreviations and Trademarks

Abbreviations

ADA	anti-drug antibody
ADCC	antibody-dependent cellular cytotoxicity
ADCP	antibody-dependent cellular phagocytosis
AE	adverse event
ALT	alanine aminotransferase
AML	acute myeloid leukemia
ANC	absolute neutrophil count
ATRA	all-trans retinoic acid
AUC	area under the concentration x time curve
BSA	body surface area
CDC	complement-dependent cytotoxicity
Cl	clearance
C _{max}	maximum concentration
CR	complete response
CRh	complete response with incomplete hematological recovery
CRi	complete response with incomplete blood count recovery
CyTOF	time of flight mass cytometry
DRC	data review committee
DNMT	DNA methyltransferase
ECG	electrocardiogram
ECOG	Eastern Cooperative Oncology Group
eCRF	electronic Case report form
ELN	European Leukemia Network
EOT	end-of-treatment
FACT-Leu	Functional Assessment of Cancer Therapy-Leukemia
FSH	follicle stimulating hormone
HIV	human immunodeficiency virus
HMA	hypomethylating agent
HRQoL	health-related quality of life
HRT	hormonal replacement therapy
ICF	informed consent form
IRR	infusion-related reaction
ITT	intent-to-treat population
IV	intravenous
LSC	leukemic stem cell
MDS	myelodysplastic syndrome
MedDRA	Medical Dictionary for Regulatory Activities
MLFS	morphologic leukemia-free state
MRD	minimal residual disease
MRU	medical resource utilization
NCI-CTCAE	National Cancer Institute Common Terminology Criteria for Adverse Events
NK	natural killer (cells)
ORR	overall response rate (CR + CRi + CRh)
OS	overall survival
PCR	polymerase chain reaction

PD	pharmacodynamics
PFS	progression-free survival
PK	pharmacokinetics
PR	partial response
PRO	patient-reported outcome
RO	receptor occupancy
SAE	serious adverse event
SC	subcutaneous
SPC	Summary of Products Characteristics
SUSAR	suspected unexpected serious adverse reaction
ULN	upper limit of normal
USPI	United States Package Insert
WBC	white blood cells

10.2. Appendix 2: Clinical Laboratory Tests

The following tests will be performed according to the Schedule of Activities by the local laboratory:

Protocol-Required Safety Laboratory Assessments

Laboratory Assessments	Parameters
Hematology	Platelet count Hemoglobin Absolute white blood cell (WBC) count Absolute eosinophils Absolute basophils Absolute monocytes Absolute neutrophil count Absolute lymphocyte count Peripheral blast count
Clinical Chemistry	Sodium Bicarbonate Potassium Blood urea nitrogen (BUN) Urea (if BUN is not performed) Creatinine Aspartate aminotransferase (AST)/Serum glutamic-oxaloacetic Alanine aminotransferase (ALT)/Serum glutamic-oxaloacetic Total bilirubin Alkaline phosphatase Lactic acid dehydrogenase (LDH) Uric acid Calcium Phosphate Magnesium
Other Screening Tests	Serum β -hCG or urine pregnancy testing for women of childbearing potential only or if clinically indicated or required by local regulations. Serology (eg, HIV antibody, hepatitis B surface antigen [HBsAg], hepatitis B virus antibody, and hepatitis C virus antibody); screening is to be performed for all participants.

10.3. Appendix 3: Regulatory, Ethical, and Study Oversight Considerations

REGULATORY AND ETHICAL CONSIDERATIONS

Investigator Responsibilities

The investigator is responsible for ensuring that the study is performed in accordance with the protocol, current International Council on Harmonization (ICH) guidelines on Good Clinical Practice (GCP), and applicable regulatory and country-specific requirements.

Good Clinical Practice is an international ethical and scientific quality standard for designing, conducting, recording, and reporting studies that involve the participation of human participants. Compliance with this standard provides public assurance that the rights, safety, and well-being of study participants are protected, consistent with the principles that originated in the Declaration of Helsinki, and that the study data are credible.

Protocol Amendments

Neither the investigator nor the Sponsor will modify this protocol without a formal amendment by the Sponsor. All protocol amendments must be issued by the Sponsor, and signed and dated by the investigator. Protocol amendments must not be implemented without prior IEC/IRB approval, or when the relevant competent authority has raised any grounds for non-acceptance, except when necessary to eliminate immediate hazards to the participants, in which case the amendment must be promptly submitted to the IEC/IRB and relevant competent authority. Documentation of amendment approval by the investigator and IEC/IRB must be provided to the Sponsor. When the change(s) involve only logistic or administrative aspects of the study, the IEC/IRB (where required) only needs to be notified.

During the course of the study, in situations where a departure from the protocol is unavoidable, the investigator or other physician in attendance will contact the appropriate Sponsor representative listed in the Contact Information page(s), which will be provided as a separate document. Except in emergency situations, this contact should be made before implementing any departure from the protocol. In all cases, contact with the Sponsor must be made as soon as possible to discuss the situation and agree on an appropriate course of action. The data recorded in the eCRF and source documents will reflect any departure from the protocol, and the source documents will describe this departure and the circumstances requiring it.

Regulatory Approval/Notification

This protocol and any amendment(s) must be submitted to the appropriate regulatory authorities in each respective country, if applicable. A study may not be initiated until all local regulatory requirements are met.

Required Prestudy Documentation

The following documents must be provided to the Sponsor before shipment of study intervention to the study site:

- Protocol and amendment(s), if any, signed and dated by the principal investigator
- A copy of the dated and signed (or sealed, where appropriate per local regulations), written IEC/IRB approval of the protocol, amendments, ICF, any recruiting materials, and if applicable, participant compensation programs. This approval must clearly identify the specific protocol by title and number and must be signed (or sealed, where appropriate per local regulations) by the chairman or authorized designee.
- Name and address of the IEC/IRB, including a current list of the IEC/IRB members and their function, with a statement that it is organized and operates according to GCP and the applicable laws and regulations. If accompanied by a letter of explanation, or equivalent, from the IEC/IRB, a general statement may be substituted for this list. If an investigator or a member of the study-site personnel is a member of the IEC/IRB, documentation must be obtained to state that this person did not participate in the deliberations or in the vote/opinion of the study.
- Regulatory authority approval or notification, if applicable
- Signed and dated statement of investigator (eg, Form FDA 1572), if applicable
- Documentation of investigator qualifications (eg, curriculum vitae)
- Completed investigator financial disclosure form from the principal investigator, where required
- Signed and dated clinical trial agreement, which includes the financial agreement
- Any other documentation required by local regulations

The following documents must be provided to the Sponsor before enrollment of the first participant:

- Completed investigator financial disclosure forms from all subinvestigators
- Documentation of subinvestigator qualifications (eg, curriculum vitae)
- Name and address of any local laboratory conducting tests for the study, and a dated copy of current laboratory normal ranges for these tests, if applicable
- Local laboratory documentation demonstrating competence and test reliability (eg, accreditation/license), if applicable

Independent Ethics Committee or Institutional Review Board

Before the start of the study, the investigator (or Sponsor where required) will provide the IEC/IRB with current and complete copies of the following documents (as required by local regulations):

- Final protocol and, if applicable, amendments
- Sponsor-approved ICF (and any other written materials to be provided to the participants)
- IB (or equivalent information) and amendments/addenda
- Sponsor-approved participant recruiting materials
- Information on compensation for study-related injuries or payment to participants for participation in the study, if applicable

-
- Investigator's curriculum vitae or equivalent information (unless not required, as documented by the IEC/IRB)
 - Information regarding funding, name of the Sponsor, institutional affiliations, other potential conflicts of interest, and incentives for participants
 - Any other documents that the IEC/IRB requests to fulfill its obligation

This study will be undertaken only after the IEC/IRB has given full approval of the final protocol, amendments (if any, excluding the ones that are purely administrative, with no consequences for participants, data or study conduct, unless required locally), the ICF, applicable recruiting materials, and participant compensation programs, and the Sponsor has received a copy of this approval. This approval letter must be dated and must clearly identify the IEC/IRB and the documents being approved.

During the study the investigator (or Sponsor where required) will send the following documents and updates to the IEC/IRB for their review and approval, where appropriate:

- Protocol amendments (excluding the ones that are purely administrative, with no consequences for participants, data or study conduct)
- Revision(s) to ICF and any other written materials to be provided to participants
- If applicable, new or revised participant recruiting materials approved by the Sponsor
- Revisions to compensation for study-related injuries or payment to participants for participation in the study, if applicable
- New edition(s) of the IB and amendments/addenda
- Summaries of the status of the study at intervals stipulated in guidelines of the IEC/IRB (at least annually)
- Reports of adverse events that are serious, unlisted/unexpected, and associated with the study intervention
- New information that may adversely affect the safety of the participants or the conduct of the study
- Deviations from or changes to the protocol to eliminate immediate hazards to the participants
- Report of deaths of participants under the investigator's care
- Notification if a new investigator is responsible for the study at the site
- Development Safety Update Report and Line Listings, where applicable
- Any other requirements of the IEC/IRB

For all protocol amendments (excluding the ones that are purely administrative, with no consequences for participants, data or study conduct), the amendment and applicable ICF revisions must be submitted promptly to the IEC/IRB for review and approval before implementation of the change(s).

At least once a year, the IEC/IRB will be asked to review and reapprove this study, where required.

At the end of the study, the investigator (or Sponsor where required) will notify the IEC/IRB about the study completion (if applicable, the notification will be submitted through the head of investigational institution).

Country Selection

This study will only be conducted in those countries where the intent is to launch or otherwise help ensure access to the developed product if the need for the product persists, unless explicitly addressed as a specific ethical consideration in Section 4.2.1, Study-Specific Ethical Design Considerations.

Other Ethical Considerations

For study-specific ethical design considerations, refer to Section 4.2.1.

FINANCIAL DISCLOSURE

Investigators and subinvestigators will provide the Sponsor with sufficient, accurate financial information in accordance with local regulations to allow the Sponsor to submit complete and accurate financial certification or disclosure statements to the appropriate regulatory authorities. Investigators are responsible for providing information on financial interests during the course of the study and for 1 year after completion of the study.

Refer to Required Prestudy Documentation (above) for details on financial disclosure.

INFORMED CONSENT PROCESS

Each participant (or a legally acceptable representative) must give written consent according to local requirements after the nature of the study has been fully explained. The ICF(s) must be signed before performance of any study-related activity. The ICF(s) that is/are used must be approved by both the Sponsor and by the reviewing IEC/IRB and be in a language that the participant can read and understand. The informed consent should be in accordance with principles that originated in the Declaration of Helsinki, current ICH and GCP guidelines, applicable regulatory requirements, and Sponsor policy.

Before enrollment in the study, the investigator or an authorized member of the study-site personnel must explain to potential participants or their legally acceptable representatives the aims, methods, reasonably anticipated benefits, and potential hazards of the study, and any discomfort participation in the study may entail. Participants will be informed that their participation is voluntary and that they may withdraw consent to participate at any time. They will be informed that choosing not to participate will not affect the care the participant will receive for the treatment of his or her disease. Participants will be told that alternative treatments are available if they refuse to take part and that such refusal will not prejudice future treatment. Finally, they will be told that the investigator will maintain a participant identification register for the purposes of long-term follow up if needed and that their records may be accessed by health authorities and authorized Sponsor personnel without violating the confidentiality of the participant, to the extent permitted by the applicable law(s) or regulations. By signing the ICF the participant or legally acceptable

representative is authorizing such access, which includes permission to obtain information about his or her survival status. It also denotes that the participant agrees to allow his or her study physician to recontact the participant for the purpose of obtaining consent for additional safety evaluations, and subsequent disease-related treatments, if needed.

The participant or legally acceptable representative will be given sufficient time to read the ICF and the opportunity to ask questions. After this explanation and before entry into the study, consent should be appropriately recorded by means of either the participant's or his or her legally acceptable representative's personally dated signature. After having obtained the consent, a copy of the ICF must be given to the participant.

Participants who are rescreened are required to sign a new ICF.

If the participant or legally acceptable representative is unable to read or write, an impartial witness should be present for the entire informed consent process (which includes reading and explaining all written information) and should personally date and sign the ICF after the oral consent of the participant or legally acceptable representative is obtained.

When prior consent of the participant is not possible and the participant's legally acceptable representative is not available, enrollment procedures should be described in the protocol with documented approval/favorable opinion by the IEC/IRB to protect the rights, safety, and well-being of the participant and to ensure compliance with applicable regulatory requirements. The participant or legally acceptable representative must be informed about the study as soon as possible and give consent to continue.

DATA PROTECTION

Privacy of Personal Data

The collection and processing of personal data from participants enrolled in this study will be limited to those data that are necessary to fulfill the objectives of the study.

These data must be collected and processed with adequate precautions to ensure confidentiality and compliance with applicable data privacy protection laws and regulations. Appropriate technical and organizational measures to protect the personal data against unauthorized disclosures or access, accidental or unlawful destruction, or accidental loss or alteration must be put in place. Sponsor personnel whose responsibilities require access to personal data agree to keep the identity of participants confidential.

The informed consent obtained from the participant (or his or her legally acceptable representative) includes explicit consent for the processing of personal data and for the investigator/institution to allow direct access to his or her original medical records (source data/documents) for study-related monitoring, audit, IEC/IRB review, and regulatory inspection. This consent also addresses the transfer of the data to other entities and to other countries.

The participant has the right to request through the investigator access to his or her personal data and the right to request rectification of any data that are not correct or complete. Reasonable steps will be taken to respond to such a request, taking into consideration the nature of the request, the conditions of the study, and the applicable laws and regulations.

Exploratory PD, biomarker, PK, and immunogenicity research is not conducted under standards appropriate for the return of data to participants. In addition, the Sponsor cannot make decisions as to the significance of any findings resulting from exploratory research. Therefore, exploratory research data will not be returned to participants or investigators, unless required by law or local regulations. Privacy and confidentiality of data generated in the future on stored samples will be protected by the same standards applicable to all other clinical data.

LONG-TERM RETENTION OF SAMPLES FOR ADDITIONAL FUTURE RESEARCH

Samples collected in this study may be stored for up to 15 years (or according to local regulations) for additional research. Samples will only be used to understand cusatuzumab, to understand AML, to understand differential intervention responders, and to develop tests/assays related to cusatuzumab and AML. The research may begin at any time during the study or the post-study storage period.

Stored samples will be coded throughout the sample storage and analysis process and will not be labeled with personal identifiers. Participants may withdraw their consent for their samples to be stored for research (refer to Section 7.2.1, Withdrawal From the Use of Research Samples).

COMMITTEES STRUCTURE

Data Review Committee

